A discontinued subject or a subject who completes the study but does not continue BRV treatment will be considered entering the Down-Titration Period only if the subject has a record of at least 1 dose of BRV after the date of EDV. The start date of the Down-Titration Period is set as 1 day after the date of EDV, and the Down-Titration Period ends on the date of the final dose of BRV (DTV).

A discontinued subject without any dosing of BRV after the EDV will not have participated in the Down-Titration Period, and no artificial Down-Titration Period will be created for the purpose of analysis.

A discontinued subject is considered to have entered the Safety Period if the subject has at least 1 contact (scheduled visit, unscheduled visit (UV), or telephone contact) after the date of the final dose (DTV). The Safety Period starts 1 day after the date of the final dose of BRV irrespective of entering the Down-Titration Period, and end date is the date of last contact with the subject.

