$$\% \text{ of days diary was done} = 100 \times \left[\frac{\text{Days since prior visit} - \text{number of days diary was not done in the interval}}{\text{Days since prior visit}} \right]$$

If one of the criteria is not fulfilled, Seizure freedom by visit is defined to be equal to 0.

Seizure freedom by visit will be based on DRC data and eCRF data collected over the Up-Titration, Evaluation and Down-Titration Period separately. All seizure types will be taken into account.

Calculation of seizure freedom by time interval

The categorical variable Seizure freedom by time interval is defined to be equal to 1 if the following criteria are fulfilled:

Criterion 1: All entered seizure codes have a count of 0 from the day after start date of appropriate time interval (i.e., not including the start date of appropriate time interval) up to and including the end date of the appropriate time interval. (If a seizure code is entered, a missing count will lead to a violation of this criteria, too.)

Criterion 2: The seizure diary was completed for at least 90% within the time interval. The percentage of days for which diary data was completed within a given 6-month interval will be calculated as follows based on a 30-day month:

$$\% \text{ of days diary was done} = 100 \times \left[\frac{180 - \text{number of days diary was not done in the interval}}{180} \right]$$

A similar calculation applies for 3-month seizure freedom based on 90 days and 12-month seizure freedom based on 360 days.

If one of the criteria is not fulfilled, Seizure freedom by time interval is defined to be equal to 0.

Seizure freedom by time interval will be based on DRC data collected over the Up-Titration, Evaluation and Down-Titration Period separately. All seizure types will be taken into account.

Calculation of Incidences for new seizure types

To calculate incidences of new seizure types and subtypes a shift table from Present at Baseline (Yes, No, Missing, Total) to Present during Evaluation Period (Yes, No, Missing, Total) will be prepared. Subjects who do not have results for subtypes at Baseline will be presented with “not assessed” Baseline results and their respective Evaluation Period result. Whenever only subtype information is available the seizure type results will be derived as follows:

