- Seizure type I is Present at Baseline = “Yes” if at least one of the subtypes IA, IB, IC is present at Baseline. It is Present at Baseline = “Missing” if data for all subtypes is missing. Otherwise, Present at Baseline = “No”.
(Same rule is to apply to summarize sub-subtypes IA1, IA2, IA3 and IA4 into IA. IA is Present at Baseline = “Yes” if at least one of the subtypes IA1, IA2, IA3 or IA4 is present at

Baseline. IA is Present at Baseline = “Missing” if data for all sub-subtypes is missing. Otherwise, Present at Baseline = “No”.)

- Seizure type II is Present at Baseline = “Yes” if at least one of the subtypes IIA, IIB, IIC, IID, IIE, IIF is present at Baseline. It is Present at Baseline = “Missing” if data for all subtypes is missing. Otherwise, Present at Baseline = “No”.
- Seizure type III does not have subtypes, so derivations are not applicable.

Incidences are the percentages for seizures which were not present at Baseline but present during Evaluation Period:

$$\text{Incidence of seizure type} = \frac{\text{Count of subjects with seizure (sub)type not present at Baseline but present in Evaluation Period}}{\text{Total number of subjects with seizure (sub)type not present at Baseline}}$$

Incidences will be calculated separately for Down-Titration Period.

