9.2 Seizure based variables based on DRC data

Absolute and percent change in 28-day adjusted seizure frequency and in 28-day adjusted POS seizure frequency will be summarized for the Evaluation Period by seizure category. This summary will present both age groups to be consistent with EEG summary and worsening based on DRC. The corresponding number and percentage of responder in reduction of 28-day adjusted seizure frequency and 28-day adjusted POS seizure frequency will be presented separately.

For subjects < 2 years of age or ≥ 2 years of age with typical absence seizures, absolute and percent worsening will be presented. Additionally, the ADF will be summarized by age group, seizure category and visit/time period.

The proportion of seizure free days over Evaluation Period will be summarized using quantitative statistics. This summary will be repeated for proportion of seizure free days by visit and by 3-month time interval (including only subjects < 2 years of age or ≥ 2 years of age with typical absence seizures).

Number and percentages of Seizure freedom will be presented over Evaluation Period. This summary will be repeated for seizure freedom by visit and by 3-month time interval (including only subjects < 2 years of age or ≥ 2 years of age with typical absence seizures).

Shift tables presenting the incidences of new seizures will be prepared to show actual occurrences of new seizures as well as the percentages based on subjects under risk (subjects without particular seizure type at Baseline).

All raw DRC data and derived efficacy variables will be listed.

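### The new-seizure-type incidence keeps subjects not observed in the period in its denominator, and counts some children of unknown Baseline status as free of the type

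*SAP*

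**What the plan says.** SAP section 3.10.3.1 (incidences for new seizure types) first describes a shift table from presence at Baseline "to Present during Evaluation Period (Yes, No, Missing, Total) will be prepared". It then gives one incidence formula:

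- numerator: "Count of subjects with seizure (sub)type not present at Baseline but present in Evaluation Period";
- denominator: "Total number of subjects with seizure (sub)type not present at Baseline".

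Section 9.2 restates the risk set as "percentages based on subjects under risk (subjects without particular seizure type at Baseline". Down-Titration gets one sentence, "Incidences will be calculated separately for Down-Titration Period", with no numerator, denominator or reference period of its own.

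Where only subtype information is available, section 3.10.3.1 derives the type from its subtypes. The type is Yes if any subtype is present. It is Missing "if data for all subtypes is missing. Otherwise, Present at Baseline" is set to No. The same rule builds IA from IA1 to IA4.

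Under section 3.2.3, a subject counts as "entering the Down-Titration Period only if the subject has a record of at least 1 dose of BRV after the date of EDV", and discontinued subjects without such a dose are given no artificial period. Table 3-1 also exempts completers who move to another brivaracetam study or to marketed drug.

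**The concern.** An incidence proportion should divide by subjects who could have been seen to develop the event. Here a subject with no diary data in the period cannot enter the numerator but stays in the denominator, and so is treated as a non-case. The plan recognises that such subjects exist, because the shift table has a Missing level after Baseline. The same section also handles the matter differently for seizure freedom: the diary-based rate is limited to subjects who entered the period and have at least one diary entry in it, and the EEG-based rate has the equivalent condition.

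The Baseline coding rule has the opposite effect. A child with IA missing and IB and IC both No is declared free of type I. If IA is then recorded in the Evaluation Period, the child is a new type I case, yet for IA itself the child's Baseline is Missing. The seizure may have been present all along.

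At stake is the table meant to show whether seizure types absent at Baseline appear on treatment. Its percentages can be pulled down by unobserved subjects and up by misclassified ones.

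**Working it through.** The plan states no incidence figure, so there is nothing to reproduce. The formulas are the plan's own. Every numerical input below is an assumption chosen to show size.

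**1. Evaluation Period denominator.** Let m be the share of Baseline-No subjects with Missing status in the period. The written formula gives (rate among those observed) × (1 − m). For a rate of 10% among those observed:

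- m = 2%: 10% × 0.98 = 9.8%
- m = 5%: 10% × 0.95 = 9.5%
- m = 10%: 10% × 0.90 = 9.0%

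The share m should be small, because the Full Analysis Set (section 3.5.3) requires a completed post-Baseline diary or EEG. It need not be zero: section 3.2.3 provides for directly enrolled subjects who never enter the Evaluation Period, and an Up-Titration diary could place them in that set.

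**2. The same formula carried to Down-Titration.** Let d be the share of Baseline-No subjects who enter Down-Titration with diary data. Let e be the share in whom the type first appeared during Evaluation, r the chance that such a type is seen again in the taper, and q the chance of first emergence in the taper among those still free of the type. Then:

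- formula as carried over: d × [q(1 − e) + r·e]
- denominator limited to those observed in Down-Titration: q(1 − e) + r·e
- also excluding subjects with earlier emergence, from numerator and denominator: q

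With q = 2%, e = 10% and r = 50%, the bracket is 0.02 × 0.90 + 0.50 × 0.10 = 0.018 + 0.050 = 6.8%. The carried-over figure is then:

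- d = 10%: 0.68%
- d = 20%: 1.36%
- d = 40%: 2.72%
- d = 100%: 6.80%

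The dilution factor is d itself. The share of the numerator already seen in Evaluation is 0.050 / 0.068 = 74%. Over e = 5 to 20% and r = 25 to 50% that share runs from 40% to 86%. With d from 10 to 100%, the carried-over figure runs from 0.32% to 11.60%, against 2.00% for first emergence in the taper. Dilution lowers the figure and carry-over raises it, so against first emergence the net direction is not fixed.

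**3. Partly missing Baseline subtypes.** Suppose true incidence is 5%, 10% of the subjects coded No have a missing subtype, and a share p of those truly had that subtype at Baseline. If every one of them shows it again in Evaluation, the reported incidence is 0.9 × 5% + 0.1 × [p + (1 − p) × 5%]:

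- p = 20%: 4.5% + 0.1 × (20% + 4%) = 6.9%
- p = 40%: 4.5% + 0.1 × (40% + 3%) = 8.8%

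For the given p these are upper bounds, because recurrence is taken as certain. If only half recur, the results are 4.5% + 0.1 × (10% + 4%) = 5.9% and 4.5% + 0.1 × (20% + 3%) = 6.8%.

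**The case against.** The strongest counter-argument concerns Down-Titration. The formula is written for the Evaluation Period, and the Down-Titration sentence says only that incidences are calculated separately. Section 3.1 has a general rule that percentage denominators follow the purpose of the analysis. Section 3.2.3 creates no Down-Titration Period for discontinued subjects who took no dose after the early discontinuation visit. A programmer could reasonably restrict the denominator unprompted. This stands to the extent that the Down-Titration defect is under-specification. It does not remove the problem, since the only formula on the page has no such restriction and section 9.2 repeats its risk set.

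A reader might go further and infer that the Down-Titration figure is wrong in its numerator too, because it re-counts types that first appeared during Evaluation and so misstates what emerges on withdrawal. The document does not support that. It never says the figure is meant to show withdrawal effects, and it defines new as absent at Baseline. On that definition, counting a type in both periods is coherent. It misleads only if the figure is read as emergence on withdrawal. It is also unclear whether the figure is tabulated: section 9 lists Down-Titration data only, unless otherwise mentioned; section 3.10.3.1 mentions these incidences, but section 9.2 names no Down-Titration table.

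Three further points stand. In the Evaluation Period the effect is probably small, and the Missing column lets a reader recompute the rate. The subtype rule applies only where no type-level result was recorded, and nothing shows how often subtypes are partly missing. The whole analysis is descriptive (section 3.1), and efficacy is exploratory (section 2).

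**Conclusion.** The point holds in a limited form. Two stated rules can each give a wrong percentage. The denominator in sections 3.10.3.1 and 9.2 has no observation condition, which conflicts with the seizure-freedom rates beside it. The Baseline rule places children of unknown status in the at-risk set whenever subtype data alone are available.

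The Evaluation Period dilution is probably slight, about 0.2 to 1.0 percentage points on a 10% rate if 2 to 10% are Missing. In Down-Titration the dilution is large if the formula is carried over, to one tenth if 10% of subjects enter and two fifths if 40% do, but that depends on a reading the plan leaves open. The inflation from partly missing subtypes depends on frequencies the plan does not give. No test or primary variable depends on this table, so the consequence is confined to how its percentages are read.

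**What to change.** - **Denominator (sections 3.10.3.1 and 9.2).** Divide by subjects without the (sub)type at Baseline who entered the period and have at least one diary entry in it, as the diary-based seizure-freedom rate already does.
- **Baseline coding.** Where a type, or IA, is derived from its subtypes, code it Missing when none is Yes and any is missing. Code it No only when all are recorded as No.
- **Down-Titration.** State that new means relative to Baseline. If emergence on withdrawal is intended instead, exclude subjects with the type in any earlier study period from both numerator and denominator. State whether the figure is tabulated or only listed.

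The cost is two or three sentences in section 3.10.3.1, a matching edit in section 9.2 and a change in table programming. No new data are needed.

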3.10.4 Direct cost parameters

Direct cost parameters will be assessed based on concurrent medical procedures, health care provider consultations not foreseen by protocol, hospital stays, and emergency room (ER) visits.

3.10.4.1 Medications (AED and non-AED)

Each medication will be classified as either an AED or a non-AED, and classification will be conducted at Data Evaluation Meetings (DEM). AED outputs will reflect AED evaluation result of concomitant Benzodiazepine from the data review meetings.

According to the time of intake, medications will be classified into five categories:

- Prior Medications: For DE subjects, prior medications include any medications that started prior to the first dose of study drug in N01266. For LTFU subjects, prior medications include any medications that started prior to the first dose in the core study.
- Previous Medications: Previous medications are a subset of prior medications. For DE subjects, previous medications include any medications that started and stopped prior to the first dose of study drug in N01266. For LTFU subjects, previous medications include any medications that started and stopped prior to the first dose in the core study.
- Medications at study entry: For DE subjects, medications at study entry include any medications taken at ScrV. For LTFU subjects, medications at study entry include any medication taken at entry of the core study.
- Concomitant Medications: Concomitant medications include any medications that were taken at least one day in common with study treatment.
- Follow-up Medications: Follow-up medications include any medication that start after final dose of study drug.

Medications can be either previous or concomitant, not both. Medications with an incomplete onset date will be classified as concomitant, and not previous, if the month and year of onset (when only the month and year are specified) is the same as the month and year of the first BRV dose or the year of onset (when only the year is specified) is the same as the year of first BRV

dose. Medications with a missing onset date will also be classified as concomitant, and not previous provided the subject received at least one dose of BRV.

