3.10 Definitions of study-specific derived variables

3.10.1 Definition of treatment-emergent AE

AEs will be classified as either pre-treatment or treatment emergent. In the following definitions, first dose of BRV refers to the first dose in N01266 (i.e., not the first dose of BRV from the core study in which subjects participated prior to N01266 for LTFU subjects). Pre-treatment AEs are defined as AEs which had an onset date at least one day prior to the first dose of BRV.

Treatment-emergent adverse events (TEAEs) are defined as AEs that had onset on or after the day of first BRV dose. AEs with an incomplete onset date will be classified as TEAEs if the month and year of onset (when only the month and year are specified) is the same or after the month and year of the first BRV dose or the year of onset (when only the year is specified) is the same or after the year of first BRV dose. AEs with a missing onset date will also be classified as TEAEs provided the subject received at least one dose of BRV.

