6.4.2 Number of previous AEDs

The number of AEDs taken prior to study entry will be summarized based on the following categorization: 0-1 AEDs, 2-4 AEDs, and ≥ 5 AEDs. Identification of medications as an AED will be done using the UCB file:

AEDs_ATCs_SEP2017_FINAL_benzo_groups_23JUL2019.xls, which reflects AED evaluation result of concomitant Benzodiazepine from the data review meetings. This summary will only include AEDs which stopped prior to study entry. In addition, this summary will also be done by seizure category.

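### SAP 3.10.4.1 labels a medication with a missing or partial start date as concomitant without checking a known stop date, against its own definitions

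*SAP*

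**What the plan says.** Section 3.10.4.1 defines the classes by timing against treatment.

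- Previous, directly enrolled (DE) subjects: "For DE subjects, previous medications include any medications that started and stopped prior to the first dose of study drug in N01266".
- Previous, long-term follow-up (LTFU) subjects: "For LTFU subjects, previous medications include any medications that started and stopped prior to the first dose in the core study".
- Concomitant: "Concomitant medications include any medications that were taken at least one day in common with study treatment".
- Exclusivity: "Medications can be either previous or concomitant, not both".

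It then sets the rule for incomplete dates. For a wholly missing start: "Medications with a missing onset date will also be classified as concomitant, and not previous provided the subject received at least one dose" of BRV. For a partial start, the medication is concomitant and not previous when the known month and year, or the known year alone, equal those of the first BRV dose.

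Section 4.2 names 3.10.4.1 as the method for missing and partial medication dates, and Section 6.4 refers back to it for the class definitions. Section 6.4.2, on the number of previous AEDs, adds its own restriction: "This summary will only include AEDs which stopped prior to study entry". Section 6.4.3 repeats that restriction.

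**The concern.** Whether a drug overlapped BRV depends on when it stopped as well as when it started. If the stop date is known and falls before the first dose, the drug cannot have overlapped, whatever its start date. The rule for incomplete dates ignores this and replaces a known answer with a default.

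At stake are the description of co-treatment (concomitant AEDs and non-AEDs by drug name) and the description of treatment history (number of previous AEDs in the categories 0-1, 2-4 and 5 or more, and previous AED use by drug name). Concomitant medication is also listed as a direct-cost parameter among the other variables in Section 2.2.3.

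**Working it through.** The SAP has no figure to reproduce here. The check applies the written rule to test records and compares the result with the section's own definitions. The first BRV dose is set at 1 June 2014 for illustration.

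| Start | Stop | Rule as written | Section's definitions |
|---|---|---|---|
| missing | March 2010 | concomitant | previous |
| missing | 31 May 2014 | concomitant | previous |
| year 2014 only | 31 May 2014 | concomitant | previous |
| missing | January 2015 | concomitant | overlap possible; default reasonable |
| missing | missing | concomitant | undetermined; default reasonable |
| January 2009 | March 2010 | previous | previous |

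The first three rows conflict. A drug that stopped before 1 June 2014 also started before then, so it meets the definition of previous and shares no day with treatment.

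**Does anything else in the SAP correct this?** The only condition on the missing-start rule is at least one BRV dose. By Section 3.5.2 every Safety Set subject meets it, so it excludes nobody in the Safety Set. No other section adds a stop-date test.

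**Concomitant tables (6.4.7, 6.4.8).** These count subjects taking each concomitant drug. A misclassified record adds its subject to that drug's row unless the subject also took the same drug during BRV. It never removes anyone, so the error can only go upwards. Section 9.3.1 relies on the same tables.

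**Previous-AED tables (6.4.2, 6.4.3).** Two readings are open.

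- If programmed from the 3.10.4.1 class, as the cross-reference in 6.4 suggests, the first two records drop out of the previous-AED count.
- If programmed from the stop date, as the restriction in 6.4.2 suggests, they stay in. They then count as previous here and as concomitant in 6.4.7, which the exclusivity sentence forbids.

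**Scale, as an assumption only.** The SAP does not say what share *m* of past AED records lack a start date. On the first reading, and with independence between records, a subject with *k* past AEDs loses at least one with probability 1 − (1 − *m*)^*k*.

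- *k* = 5 (leaves the top category): 1 − 0.95^5 = 0.226 for *m* = 5%; 1 − 0.90^5 = 0.410 for 10%; 1 − 0.80^5 = 0.672 for 20%.
- *k* = 2 (falls to 0-1): 0.098, 0.190 and 0.360 for the same shares.

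On the second reading the loss is zero at every *m*. The result therefore depends on an unresolved reading as well as an unknown share.

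**The case against.** The strongest reply is that the previous-AED counts may not be harmed at all. Sections 6.4.2 and 6.4.3 state their own selection by stop date, and an AED with no start date and an early stop satisfies it. A reader might infer from 3.10.4.1 that a child with five past AEDs, two of them without a start date, slides from the top category to 2-4. The SAP does not establish that, because on the plain wording of 6.4.2 the child stays where he or she is. This part of the reply stands. What remains for those tables is an inconsistency between sections, not a demonstrated loss.

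Other parts also stand. The tables of AEDs at study entry (6.4.5, 6.4.6) rest on a separate class and are unaffected. Nothing in the SAP shows that start dates of old AEDs are often missing. The rule touches any stopped drug, not only those that failed; Section 6.4.4 lists remission and adverse drug reaction among the reasons for stopping. Section 9.3.1 only points to the medication tables, so no cost or duration figure is distorted. All summaries are descriptive and all medications are listed.

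It could also be said that defaulting to concomitant is conservative. That holds when overlap is possible. It does not hold when a recorded stop date rules overlap out, so this argument does not rescue the rule.

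A parallel might be drawn with adverse events: "AEs with a missing onset date will also be classified as TEAEs provided the subject received at least one dose of BRV". That rule ignores a resolution date before the first dose in the same way. For a safety variable, however, over-inclusion is a cautious default, and no material effect can be shown from the SAP.

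**Conclusion.** The rule is wrong as written for one identifiable set of records: medications whose start date is missing, or partial and matching the first-dose month or year, and whose known stop date precedes BRV. For these it contradicts the definitions in its own section. The concomitant AED and non-AED tables are overstated by whatever number of such records exists, less those where the subject also took the same drug with BRV. The previous-AED tables are left open to two incompatible programs, one that loses the records and one that breaches exclusivity.

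The number affected cannot be derived from the SAP. The probabilities above rest on an assumed share of missing start dates, on independence and on one of the two readings, so they should not be quoted as an estimated effect. No primary or secondary variable uses the classification. The point is worth correcting because it is clear-cut and cheap to correct; it does not threaten the study's main conclusions.

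**What to change.** In Section 3.10.4.1, place a stop-date test ahead of the rules for both missing and partial start dates:

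- If the stop date, or the latest date compatible with a partial stop date, is before the first dose, classify the medication as previous and not concomitant. The reference is the first dose in N01266 for DE subjects and the first dose in the core study for LTFU subjects, as in the existing definition of previous.
- Otherwise, or if the medication is ongoing or its stop date is missing, apply the present rule.

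This brings the class into line with the stop-date selection in 6.4.2 and 6.4.3 for these records, so they no longer appear on both sides. The cost is a sentence or two in the SAP and one condition in the derivation, with no new data. Adding the same test to Section 3.10.1 for adverse events that resolved before the first dose is an optional, minor consistency step.
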